10.4 Analysis Population

Statistical analyses will be conducted on all randomized subjects who have successfully completed the study without a protocol deviation that is regarded as impacting the assessment of the primary hypothesis (as per protocol). Missing data will be excluded from the analysis and will not be extrapolated from the collected data.

10.5 Descriptive Statistics

Descriptive statistics will be reported at dispensing and each follow-up visit. Continuous variables will be summarized using mean, standard deviation, and range; and categorical data variables will be summarized using percent frequency distribution, mean, and SD. Nominal variables will be summarized using percentages.

Summaries will be presented by control group for each lens type.

10.6 Data Pooling

Data will be pooled from multiple study sites for this analysis, the basis for pooling comes from three factors:

- The study sites must implement one common protocol.
- VCR must closely monitor study site protocol compliance.
- The study sites must use common data collection procedures.

10.7 Primary Statistical Analysis

Comfort scores at the final follow-up visit will be analysed using a mixed linear model. The model will include the following fixed effects: lens type, control group, site, and the interaction of lens type by control group; and subject nested in site as a random effect. The least-square means and their differences will be reported with 95% confidence intervals for each lens type

by control group. Conclusions will be drawn from the 95% confidence interval of the least-square mean differences.

10.8 Secondary Statistical Analysis

The secondary variables will be analysed using mixed linear models. The models will include the following fixed effects: lens type, control group, site, and the interaction of lens type by control group; and subject nested in site as a random effect. The least-square means and their differences will be reported with 95% confidence intervals for each lens type by control group. Conclusions will be drawn from the 95% confidence interval of the least-square mean differences.

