### 3.4 Secondary Outcome Hypotheses

- i. Average wearing time will be longer with Avaira Vitality than the control contact lenses at the final visit.
- ii. Comfortable wearing time will be longer with Avaira Vitality than the control contact lenses at the final visit.
- iii. Pre-lens tear film quality will be better with Avaira Vitality than the control contact lenses at the final visit.
- iv. Film deposits will be better with Avaira Vitality than the control contact lenses at the final visit.
- v. White spot deposits will be fewer with Avaira Vitality than the control contact lenses at the final visit.
- vi. Overall lens fit acceptance will be better with Avaira Vitality than the control contact lenses at the final visit.

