**Table 4: Sample size calculation.**

| Comfort  |      |      |      |
|--|------|------|------|
| Scale  | 0-10 |      |      |
| Type I (a)                                       | 5%   |      |      |
| Power (1-b)                                      | 80%  |      |      |
| SD of difference between pairs ( $\sigma$ )      | 1.9  |      |      |
| Minimum detectable difference (T-C) ( $\delta$ ) | 0.50 | 0.75 | 1.00 |
| Minimum size per group (Inequality)              | 116  | 53   | 31   |

N.B. Calculations performed using Hintze, J. (2013). PASS 12. NCSS, LLC. Kaysville, Utah, USA. [www.ncss.com](http://www.ncss.com).

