**Secondary:**

The following variables will be the secondary end-points:

- i. Wearing time: Average WT & Comfortable WT [hrs]
- ii. Surface wetting: Pre-lens tear film quality [0-4]
- iii. Deposits: Film deposits [0-4]
- iv. White spot deposits [no.]

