## v. Overall lens fit acceptance [0-4].

10.3 Statistical Considerations

All statistical analyses will be performed using the SAS software Version 9.4 or later (SAS Institute, Cary, NC).

The final analysis will be completed after all subjects have been exited from the study, all queries have been resolved, and the database has been locked.

The overall type I error rate will be preserved at 5%. All tests will be two-sided. The primary hypothesis must be met in order to satisfy the objective of this study.

From the insertion and removal times the average wearing time will be calculated. If the subject indicates that lens comfort deteriorates during wear, the comfortable wearing time will be calculated from the insertion time and the time that lenses become uncomfortable. If there is no deterioration in comfort then the average wearing time will be used [REDACTED]

Data from unscheduled visits will not be included in the analysis.

Any deviations from this analysis plan will be detailed in the study report.

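### White-spot counts are judged from a model with one residual variance for both control groups, so the interval is too narrow in one group and too wide in the other if deposit levels differ

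*Combined protocol and SAP*

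**What the plan says.** Section 10.2 lists white spots among the secondary end-points and records them as a number. Section 3.4 gives them their own directional hypothesis (item v): "White spot deposits will be fewer with Avaira Vitality than the control contact lenses at the final visit".

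Section 10.8 covers all secondary end-points with one rule: "The secondary variables will be analysed using mixed linear models". The terms are "lens type, control group, site, and the interaction of lens type by control group; and subject nested in site as a random effect". The decision rule is "Conclusions will be drawn from the 95% confidence interval of the least-square mean differences", reported for each lens type by control group. Section 10.3 adds "All tests will be two-sided" and an overall type I error of 5%.

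For white spots the plan names no count distribution, transformation, assumption check, fallback or group-specific variance. Section 10.9 allows other appropriate methods, but only for other selected variables.

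By design the two control groups differ. Biomedics 55 Premier subjects wear each lens for 4 weeks, and Acuvue 2 subjects wear each lens for 2 weeks (section 7.2.1).

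**The concern.** The contrasts are reported separately by control group, but their standard errors come from one pooled residual variance. For a count, a group that accumulates more spots will normally also have more variable differences. Pooling then understates the uncertainty in that group and overstates it in the other.

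Two opposite errors follow. In the high-count group, hypothesis v could be declared met too easily. In the low-count group, a real reduction could be almost undetectable. The different control lenses and wear periods make unequal deposit levels plausible. The documents do not show that they will occur, or which group would have more.

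**Working it through.** **Inputs from the documents.** 50 subjects per group with 10% discontinuation (section 10.1) gives 50 × 0.9 = 45 pairs per group. The analysis is in completers without imputation (10.4), two-sided at 5% (10.3).

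**The plan's own figure.** Table 4 gives 116, 53 and 31 subjects per group for comfort differences of 0.50, 0.75 and 1.00, with 1.9 as the "SD of difference between pairs". A two-sided paired t-test by the noncentral t distribution at 80% power gives 116, 53 and 31 exactly. That table is for comfort only. The plan has no white-spot figure to reproduce.

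**What the planned model computes.** Let D be test minus control for one subject. In complete paired data the lens contrast in group g is the mean of D in that group, and its standard error is √(s²/n). Here s² = (s_A² + s_B²)/2 when both groups have n = 45, on 44 + 44 = 88 degrees of freedom. One generated data set fitted as a mixed model with site gave a standard error of 1.046, the same as this formula.

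**Effect of unequal variance.** Let r be the true variance of D in the high-count group divided by that in the low-count group. The ratio k of the planned to the correct standard error is about √((1 + 1/r)/2) in the high-count group and √((1 + r)/2) in the low-count group. With no lens effect, the chance of a false finding of fewer spots is about Φ(−1.96k), and coverage is about 2Φ(1.96k) − 1.

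To get r, assume that prevalence and count-when-present in the second group are both f times those in the first. The leading term of the variance is prevalence × count², so r is about 1/f³.

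| f | r | k, high group | False 'fewer' | Coverage | k, low group | False 'fewer' | Coverage |
|---|---|---|---|---|---|---|---|
| 1 | 1 | 1 | 2.5% | 95% | 1 | 2.5% | 95% |
| 0.75 | 2.37 | 0.843 | 4.9% | 90% | 1.298 | 0.5% | 99% |
| 0.5 | 8 | 0.750 | 7.1% | 86% | 2.121 | about 0% | about 100% |

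The harm in the high-count group is bounded. As r grows without limit, k tends to √0.5 = 0.707, which gives 8.3% and 83%.

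**Simulation (assumed distributions).** Zero-inflated overdispersed counts, 45 pairs per group, 4,000 runs, 30% prevalence on both lenses, mean 4 spots when present:

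- Groups alike: false 'fewer' 2.4–2.6%, coverage 95%.
- Second group at three-quarters: about 5% and 91% in the high-count group.
- Second group at half: 7.1% and 86% in the high-count group, 0.0% and 100% in the other.
- A paired t-test with each group's own variance, and the signed-rank test, stayed at 2.2–2.8%.
- Where a real lens effect was added at the half level, power in the low-count group was about 1% with the planned model and 19–29% with that group's own variance.

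**A second generator.** Poisson-gamma counts with mean 2 in one group and 0.5 in the other, no lens effect, gave two-sided error 0.13–0.15 in the high-count group and 0.000–0.003 in the other. Coverage was 0.85–0.87 and about 1.00. The formula agrees. With gamma shape 1.5 and independent lenses, the variances per lens are 2 + 4/1.5 = 4.667 and 0.5 + 0.25/1.5 = 0.667. So r = 7, k = √((1 + 1/7)/2) = 0.756, and the two-sided error is 2Φ(−1.482) = 0.138, against 0.142 simulated.

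**Zeros alone.** With the same Poisson-gamma distribution in both groups and 46–79% zeros, two-sided error was 0.038–0.056. Coverage under a true difference was mostly 0.92–0.96, falling to 0.90 only with extreme skew.

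**The case against.** The strongest reply is that the documents give no mean, zero share or spread for white spots, and that the planned test works when the two groups have similar counts. That is correct, and it limits the point to a conditional one. The condition does follow from the design, since exposure time and control lens both differ by group.

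A reader might infer three stronger things that the documents and the check do not support:

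- *That many zeros break the model.* No section says the count is zero-heavy, and at 45 pairs per group zeros alone did not disturb the error rate.
- *That the plan is anti-conservative in general.* The inflated error is in the high-count group only. The other group has the opposite error.
- *That a paired rank test is more powerful.* This depends on the distribution. With like groups, the signed-rank test was ahead in one setting (0.63 against 0.51), slightly behind in another (0.29 against 0.31), and clearly behind when only the number of spots fell and prevalence did not (0.15 against 0.24). With unequal groups, the planned model can reject more often in the high-count group (0.51 against 0.33), but only because its interval is too narrow.

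It can also be said that section 10.3 lets deviations from the plan be described in the report. That permits a later change, but it does not pre-specify one. Finally, a signed-rank test drops the site term and does not estimate the mean difference, so it is a weak choice as the sole replacement. That objection stands and shapes the fix.

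**Conclusion.** The point holds as a conditional weakness. The shared residual variance miscalibrates the white-spot interval in both directions whenever deposit variability differs between control groups. At half the prevalence and count in the second group, the false 'fewer' rate in the high-count group is about 7% against 2.5%. At three-quarters it is about 5%, and in the limit 8.3%. In the low-count group the cost is power.

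These figures rest on assumed count distributions, 45 complete pairs per group, and one value per subject and lens. The readable text does not say how the two eyes are combined.

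The consequence is minor. It concerns one of six secondary hypotheses, and section 10.3 ties the study objective to the primary hypothesis alone, so the primary conclusion is untouched.

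**What to change.** In section 10.8, state that for white spots the conclusion in each control group rests on a method that uses that group's own variance. Either of these will do:

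- the planned model with a control-group-specific residual variance, which in effect is a within-group paired analysis and keeps the site term and the mean difference; or
- a negative-binomial GEE clustered by subject, with control-group-specific dispersion.

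Add the within-group Wilcoxon signed-rank test as a supporting analysis. Report the count distribution and the proportion of subjects with any spot, by lens and control group.

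The cost is a sentence or two in 10.8 and a few lines of SAS. Degrees of freedom fall from 88 to about 44 per contrast, which moves the critical t value from 1.99 to 2.02. The signed-rank test is not site-adjusted and gives no mean difference, which is why it is supporting only.

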10.9 Additional Statistical Analysis

Other selected variables may be analysed using appropriate statistical methods. A *P*-value less than or equal to 0.050 will be regarded as statistically significant.

10.10 Interim Analysis

There are no planned interim analyses for this study.

---

## 11 GENERAL STUDY MANAGEMENT

---

11.1 Relevant Standards

This protocol has been developed in accordance with the following:

- ISO 14155-1:2011 Clinical Investigation of Medical Devices for Human Subjects
- ISO 11980:2012 Contact Lenses and Contact Lens Care Products – Guidance for Clinical Investigations.
- ICH Harmonized Tripartite Guideline for Good Clinical Practice
- Declaration of Helsinki

The study will also be carried out in accordance with the VCR Quality Management System (ISO 9001:2015) and all the applicable local guidelines.

11.2 Ethics Review

The study protocol, Participant Information Sheet and Informed Consent Form and all other required documents will be submitted to Sterling IRB for each site. A favorable opinion will be received prior to undertaking the study.

If significant protocol changes which require the preparation of an amendment are necessary, written IRB approval will be obtained prior to implementation.

11.3 Protocol Deviations

The Investigators will not deviate from the protocol without written approval from the IRB and VCR.

In medical emergencies, Investigators will use their judgement and remove the subject from immediate hazard. Any significant changes or deviations in the protocol will be the subject of a protocol amendment and must be pre-approved by the IRB.

If an unexpected deviation from the protocol occurs the Investigator must notify the VCR immediately and the deviation from the protocol will be reported on a Protocol Deviation form in EDC and appropriate action taken.

#### 11.4 Premature Termination of the Study

The sponsor reserves the right to terminate the study at any time for any reason including adverse effects. If it is determined that an unanticipated adverse device effect presents an unreasonable risk, then the entire investigation or part of the investigation presenting the risk shall be terminated as soon as possible. A written statement fully documenting the reasons for such termination will be provided to the IRB.

#### 11.5 Source Documentation

Unless otherwise documented, the eCRFs will be considered the source document. The sponsor or sponsor's representatives will be authorized to gain access to the source documentation for the purposes of monitoring and auditing the study (See Sections 11.6, 11.7).

The Source Document Record must be completed to comply with GCP guidelines. It is a permanent record within the patient's chart/notes that documents the subject's involvement in a clinical research study.

Contents of the source document record:

- Study number
- Subject ID
- Confirmation that subject met eligibility criteria
- Confirmation that subject signed the informed consent
- Confirmation that subject received a signed and dated copy of informed consent
- Date enrolled
- Details of lenses worn on study
- General notes
- Adverse events
- Reportable Protocol deviations
- Exit date
- Whether subject completed the study or discontinued
- Investigator's signature

The Source Document Record will be completed for each subject upon enrolment and then updated when required, e.g. when subject exits the study.

#### 11.6 Monitoring

Investigational site monitoring will be performed by a qualified study monitor identified by the sponsor or VCR. On-site visits will be completed at each site. The frequency and procedure of the monitoring visits will be documented in the Monitoring Plan which is in a separate document. The Investigator will allow the study monitor and sponsor representatives or IRB to observe procedures and inspect study records and subjects' medical records throughout the study to verify protocol compliance, case report completeness, and investigational material accountability. Should the Investigator be found to be non-compliant and unwilling or unable to convert noncompliant practices, VCR in consultation with the sponsor will terminate the Investigator's role in the investigation and the IRB will be notified.

**11.7 Audits**

The Investigator shall permit VCR, the sponsor and the IRB to inspect its facilities, equipment, and study-related records, data and other documents upon reasonable notice. In addition, the IRB may conduct such inspections as they deem necessary at any time whether or not advanced notice is given by them. The Investigator agrees to notify the sponsor or VCR within 24 hours (or as soon as reasonably practicable) of the start of any unannounced inspection by the IRB or of the receipt from the IRB of a notice of inspection whether given in writing or orally. If such notice is in writing, a copy with any attachments thereto shall be provided to VCR or the sponsor.

**11.8 Records Retention**

According to the ICH GCP guidelines the essential documents should be retained until at least two years after the last approval of a marketing application in an ICH region and until there are no pending or contemplated marketing applications in an ICH region or at least two years have elapsed since the formal discontinuation of clinical development of the investigational product. It is the responsibility of the sponsor to inform the Investigator/institution as to when these documents no longer need to be retained. The study lens material is already on the market and therefore the study documents should be kept for a minimum of two years after the end of the study. As the clinical research organization supervising the study, VCR will also retain the written records for the same period of time. Following such retention period, the Investigator or the Clinical Site shall deliver to the sponsor all such Research Results, unless otherwise instructed in writing by the sponsor. Notwithstanding the foregoing, all information provided by or with respect to subjects in the Study will be furnished by Investigator and Clinical Site without patient names.

**11.9 Confidentiality and Publication**

This study is confidential in nature. The Investigator shall make no public statement, whether in written, oral or electronic form, relating to the VCR, the Sponsor, the substances, materials, products and devices being investigated or the Study itself without obtaining the prior written consent of the VCR or the Sponsor.

All information gathered during this study is proprietary and should be made available only to those directly involved in the study who have a need to know.

Authorized recipients of this data include:

- Investigator and co-investigator(s)
- Other allied health care personnel necessary for the conduct of the study
- IRB personnel
- Sponsor representatives
- Contract Research Organization
- Designated study monitor
- Designated medical monitor
- FDA or other government regulatory agencies

All above personnel who are provided with data concerning this study will be informed of its confidential and proprietary nature. Release of this data (through presentation, publication or other written or oral communication) to other than the above listed personnel requires the prior written permission from the study Sponsor. Study investigators and all office personnel are prohibited from acknowledging participation in the study to individuals and organizations except those listed above. This includes sales representatives and other departments or subsidiaries of the sponsor without the direct written permission of the sponsor.

The study will conform to the requirements of the Health Information Portability and Accountability Act (HIPAA). By signing the authorization to use and disclose protected health information the subject authorizes the sponsor and the sponsor's representatives (VCR) to access their optometric clinical records. This authorization will expire 50 years from the date the subject signs. Subjects will have the right to reverse this authorization at any time.

All patient information will have the patient name (or any information that can identify the patient apart from the mobile phone number) removed before leaving the Principal Investigator's site.

In accordance with the VCR Confidentiality Policy, the data, information, and reports arising from this project are the property of the sponsor company. By signing the Informed Consent Form the subject also understands that their data will be sent to VCR in the UK and the sponsor in the US. VCR will not release to a third party any information arising from this study unless required to do so by a legal or regulatory body. The electronic records will also be handled in accordance with Health Information Portability and Accountability Act (HIPAA).

The study will be registered on the website [www.clinicaltrials.gov](http://www.clinicaltrials.gov).

**APPENDIX A**

The figure consists of a 6x3 grid of 18 sub-images. Each sub-image is a black and white pattern of horizontal bars. The patterns vary in the number of bars, their lengths, and their vertical positions. Some patterns are more complex, featuring multiple bars of different heights, while others are simpler, such as a single long bar or a few short bars. The overall arrangement is a 6x3 grid.

[figure not shown]
The figure consists of a 6x3 grid of horizontal bar charts. The bars are black on a white background. The first two columns have solid black bars, while the third column has dashed black bars. The length of the bars varies across the grid, indicating different data values. The bars are grouped by row, with each row containing one bar from each column.

A 6x3 grid of 18 black bars of varying lengths and positions. The bars are arranged in 6 rows and 3 columns. The lengths of the bars decrease from left to right in each row. The positions of the bars also change, with some bars appearing in the first column and others in the third column. The bars are black on a white background.

**MEASUREMENT INSTRUCTIONS**

**MEASUREMENT INSTRUCTIONS**

A horizontal bar chart consisting of 15 black bars of varying lengths. The bars are arranged in a descending order of length from left to right. The first bar is the longest, and the last bar is the shortest. The bars are set against a white background with a thin black horizontal line at the top.
